10.2.5. Overall Survival

OS will be defined as the time from commencement of therapy until death from any cause. Patients will be followed with a telephone call or clinic visit every 3 months for years 1-3 for survival status. The cause of death will be documented if known and relationship to study drug as per section 9.3.2. OS for patient treated with neoadjuvant chemoradiation prior to surgery in patients with stage III NSCLC was a median of 23.6 months as reported by Albain and colleagues. We anticipate to see similar or potentially improved results in this study.

18-Nov-2020 Page **113** of **164**

IND #134339

11. Study Drug Information

11.1. Durvalumab and Tremelimumab

12. Statistical Methods and Sample Size Determination

12.1. Study Design

This is an open-label pilot study aimed at establishing the safety and feasibility of neoadjuvant immunoradiation prior to surgical resection of stage III NSCLC, that is deemed surgically resectable by a thoracic surgeon with lobectomy. Thoracic RT will be given at standard doses and fractionation to a total dose of 45Gy in 25 fractions, as per published phase III data⁴⁹, and using standard methods. In cohort 1, the safety and feasibility of durvalumab with concurrent thoracic RT, will be assessed. In this cohort, durvalumab will be administered at the standard dose of 1500mg IV every 4 weeks for 3 doses, as per ongoing phase III studies. If preliminary safety is established in cohort 1, the study will expand to include cohort 2, which will test the safety and feasibility of durvalumab plus tremelimumab with concurrent thoracic RT. In this cohort, durvalumab will be administered at the standard dose of 1500mg IV every 4 weeks for 3 doses, and tremelimumab will be administered at the standard dose of 75mg every 4 weeks for 3 doses. The primary endpoints of this study are safety and feasibility in cohort 1 and cohort 2 (if applicable). Patients will be observed for perioperative grade 3-4 adverse events through day 90 following the last dose of immunotherapy or until 30 days post-surgery, whichever is longer. Safety and feasibility will be monitored continuously throughout the study through weekly meetings with investigators, as well as the planned Bayesian monitoring rules (see below). A set of markers of immune reactivity measured in lung tumor resection specimens, draining lymph nodes, and peripheral blood will be evaluated. Feasibility will be evaluated as the proportion of evaluable patients who successfully complete preoperative treatment and proceed to surgery without any extended treatment related delays. Extended treatment-related delay will be defined as >8 weeks from the day of completion of thoracic RT. For each cohort, we aim to accrue 16 evaluable patients, defined as those who receive at least one dose of durvalumab or durvalumab/tremelimumab administration and have complete toxicity follow-up. We plan to accrue 20 patients to ensure 16 evaluable patients are available for analysis. If less than 16 evaluable patients are available after accruing 20 patients, we will amend the protocol to ensure at least 16 evaluable patients are available for analysis.

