3.1.2. Determination of Eligibility

After eligibility is established, the study staff will register participants. The following are required to be submitted for successful registration:

Registration forms 🔛

Copy of subject consent 🔛

Copies of the following documents:

- Diagnostic pathology report(s) [SEP]
- PET/CT or CT scan report, MRI or CT brain with contrast report
- Laboratory reports including: [stp]

o Complete blood count (CBC) with differential (including absolute lymphocyte count) and direct platelet count.

18 Nov 2020 Page **55** of **164**

- o Chemistry: Albumin, SGOT (AST), SGPT (ALT), Bilirubin (direct and total), Calcium, Creatinine, Glucose, Total protein, Urea nitrogen, Uric Acid, Electrolytes (including sodium, potassium, chloride and bicarbonate).
- o Liver function tests (AST, ALT, Total bilirubin, alkaline phosphatase)
- o Urinalysis (routine)
- o Baseline thyroid immune safety assay: Thyroid Stimulating Hormone (TSH). Abnormal endocrine results should be followed up per standard of care, and may require an endocrine consult and additional testing.
- o Pulmonary function report
- o Other documents, if requested.

Study treatment cannot begin until the patient is registered. Subjects who sign a consent form, but do not initiate protocol treatment for any reason (e.g., subjects who are screen failures), will be replaced and will not count towards our accrual goal. Also patients who do not stay enrolled through the DLT period, will be replaced and not count towards our accrual goal.

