4.4. Permanent Discontinuation of Study Therapy

An individual subject will not receive any further investigational product if any of the following occur in the subject in question:

Withdrawal of consent or lost to follow-up

Adverse event that, in the opinion of the investigator or the sponsor, contraindicates further dosing

Subject is determined to have met one or more of the exclusion criteria for study participation at study entry and continuing investigational therapy might constitute a safety risk

Pregnancy or intent to become pregnant

Any AE that meets criteria for discontinuation as defined in Section 9.3.

- Serious Adverse event related to thoracic radiation, with the exception of toxicities that do not meet the criteria for discontinuation as defined in Section 9.3.
- Dose-limiting toxicity (See Section 6.3 for definition of DLT).
- Grade ≥ 3 infusion reaction

18 Nov 2020 Page **64** of **164**

- Subject noncompliance that, in the opinion of the investigator or sponsor, warrants withdrawal; e.g., refusal to adhere to scheduled visits
- Initiation of alternative anticancer therapy including another investigational agent
- Confirmation of PD and investigator determination that the subject is no longer benefiting from treatment with durvalumab
 + tremelimumab

Subjects who are permanently discontinued from further receipt of investigational product, regardless of the reason (withdrawal of consent, due to an AE, other), will be identified as having permanently discontinued treatment.

Subjects who are permanently discontinued from receiving investigational product will be followed for safety per Section 9.0 and Appendix 2 or 3, including the collection of any protocol-specified blood specimens, unless consent is withdrawn or the subject is lost to follow-up or enrolled I another clinical study. All subjects will be followed for survival. Subjects who decline to return to the site for evaluations will be offered follow-up by phone every 3 months as an alternative.

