6.3. Definition of Dose Limiting Toxicity (DLT)

Dose-limiting toxicities (DLTs) will be evaluated from the first day of administration of durvalumab (cohort 1) or durvalumab+tremelimumab (cohort 2), in this trial. The period for evaluating DLTs will be from the day of first administration of study therapy until 30 days after surgical resection or 100 days following the last dose of study therapy, whichever occurs later. Subjects who do not remain on the study up to this time for reasons other than DLT will be replaced with another subject. Grading of DLTs will follow the guidelines provided in the Common Terminology Criteria for Adverse Events (CTCAE) version 4.0. A patient who experiences a DLT will be permanently discontinued from treatment and will proceed to surgery after standard preoperative evaluation by a surgeon and anesthesiologist. Prior to surgery any treatment related toxicity should have resolved to ≤grade 1. [5]

A DLT will be defined as any Grade 3 or higher toxicity that occurs during the DLT evaluation period. Toxicity that is clearly and directly related to the primary disease or to another etiology is excluded from this definition. The following will be DLTs:

- Any Grade 4 irAE
- Any ≥ Grade 3 colitis
- Any Grade 3 or 4 non-infectious pneumonitis irrespective of duration
- Any Grade 2 pneumonitis that does not resolve to ≤ Grade 1 within 3 days of the initiation of maximal supportive care
- Any Grade 3 irAE, excluding colitis or pneumonitis, that does not downgrade to Grade 2 within 3
 days after onset of the event despite optimal medical management including systemic
 corticosteroids or does not downgrade to ≤ Grade 1 or baseline within 14 days
- Liver transaminase elevation > 8 × ULN or total bilirubin > 5 × ULN
- Any ≥ Grade 3 non-irAE, except for the exclusions listed below

The definition excludes the following conditions:

- Grade 3 fatigue lasting ≤ 7 days
- Grade 3 endocrine disorder (thyroid, pituitary, and/or adrenal insufficiency) that is managed
 with or without systemic corticosteroid therapy and/or hormone replacement therapy and the
 subject is asymptomatic
- Grade 3 inflammatory reaction attributed to a local antitumor response (e.g., inflammatory reaction at sites of metastatic disease, lymph nodes, etc.)
- Concurrent vitiligo or alopecia of any AE grade
- Grade 3 infusion-related reaction (first occurrence and in the absence of steroid prophylaxis) that resolves within 6 hours with appropriate clinical management

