12.2.2. Safety Endpoint

Safety stopping rule:

To minimize the risks of adding durvalumab monotherapy (cohort 1) or durvalumab+tremelimumab (cohort 2) to thoracic radiation prior to surgery, safety will be monitored by a Bayesian stopping rule for the rate of adverse events of interest (Section 9.2). Previous experience with single and multiple dose schedules of durvalumab and durvalumab+tremelimumab demonstrated that the incidence of grade 3-4 toxicities in advanced NSCLC and other solid tumors is low. The primary DLTs of concern for safety monitoring will be grade 3-4 toxicities of the types listed in section 6.3. These include liver, GI, renal, pneumonitis and any other grade 3-4 toxicity that in the opinion of the investigator significantly interfered with the subjects' optimal perioperative management. They will be monitored continuously for sixteen patients through day 90 following the last dose of immunotherapy (or day 30 post-surgery, whichever is longer).

AEs will be monitored continuously for all patients. A Bayesian safety monitoring rule will be used to evaluate the rate of the AE of interest continuously, from the 3rd evaluable patient, and will suspend accrual at any point if there is sufficient evidence of excessive toxicity. Specifically, the Bayesian toxicity monitoring rule will suspend accrual anytime if the posterior probability of AE of interest being larger than 25%, is 70% or higher. We assume a priori that the experimental regimens has an average risk around 5% and there is about 7% chance that the risk will be 25% or higher. This corresponds to a Beta (0.05,0.95) prior distribution. Table 10.1 summarizes the continuous stopping rule for the 16 evaluable patients for each regimen. For example, if 2 patients out of the first 3 or 4 evaluable patients experience adverse events of interest, we will stop accrual. Furthermore, to cautiously assess the toxicity profiles of experimental regimens in the event that accrual is relatively "fast" comparing to the safety assessment duration, the accruals of each cohort will be suspended when 6 eligible patients have been accrued to allow the continuous safety evaluations to be done among the first 6 evaluable patients before further accruals. The accrual would resume only if the following Bayesian stopping rule being used is not met. At any time if the stopping criterion is met, accrual to the trial will be temporarily suspended and the

18-Nov-2020 Page **115** of **164**

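### The safety stopping rule has conflicting denominators, and section 12.1 has no clause that keeps a patient with an observed DLT in the count; the replacement rules also conflict

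*Combined protocol and SAP*

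**What the plan says.** **Who is counted for safety.** Section 12.1 defines evaluable patients as "defined as those who receive at least one dose of durvalumab or durvalumab/tremelimumab administration and have complete toxicity follow-up" and plans 20 accrued so that 16 evaluable patients can be analysed. Section 12.2.2 states that "Table 10.1 summarizes the continuous stopping rule for the 16 evaluable patients for each regimen", and starts monitoring at the third evaluable patient. The synopsis speaks instead of the rate among all treated patients, and the denominator row of Table 10.1 is labelled as patients treated. The matching row of Table 10.3 is labelled as evaluable patients. Section 12.3.1 reports proportions with exact intervals but names no denominator.

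**Monitoring.** Section 12.2.2 also says "AEs will be monitored continuously for all patients", and that "At any time if the stopping criterion is met, accrual to the trial will be temporarily suspended".

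**Follow-up.** Section 4.4 continues safety follow-up after treatment is stopped, "unless consent is withdrawn or the subject is lost to follow-up" or enters another study.

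**Replacement.**
- Section 3.1.2: "Also patients who do not stay enrolled through the DLT period, will be replaced and not count towards our accrual goal".
- Section 4.2, item 27: withdrawn patients are not replaced. Section 4.6: they are.
- Section 6.3: "Subjects who do not remain on the study up to this time for reasons other than DLT will be replaced with another subject".
- Sections 6.2.2.5, 6.2.3.1 and 6.2.3.3: patients with incomplete radiation, suitable only for pneumonectomy after therapy, or with missed doses before surgery are replaced but still followed for safety.

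**Feasibility.** Sections 12.1 and 12.2.1 require that preoperative treatment be completed and that surgery follow without extended treatment-related delay. The event row of Table 10.5 counts only delays in planned surgery.

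**The concern.** A stopping rule needs a single, unambiguous numerator and denominator. Here a patient's event can be known, yet the patient can fail the evaluable definition because follow-up ended early. Section 4.4 narrows this to patients who withdraw consent, are lost, or enter another study.

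Section 6.3 gives partial protection, because it replaces only those who leave for reasons other than a DLT. But it governs replacement, not counting, and it does not cover a patient who has a DLT and later leaves for some other reason. Sections 3.1.2 and 6.2.3.3 carry no such exception. Section 6.3 also says "A patient who experiences a DLT will be permanently discontinued from treatment and will proceed to surgery", so a DLT before the third dose leads directly into the missed-doses rule of 6.2.3.3. No section says whether a replaced patient stays in the safety or feasibility counts.

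With 16 patients per cohort, one event can decide whether accrual is suspended. Cohort 2 opens on the safety of cohort 1, so the count matters beyond one cohort.

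**Working it through.** **Inputs.** From 12.2.2: prior Beta(0.05, 0.95); suspend if P(rate > 25%) is at least 70%; looks at each n from 3 to 16. From 12.2.3: prior Beta(0.1, 0.9) for a surgery failure; pause if P(failure rate > 25%) exceeds 70%; looks from n = 6. All patient counts and loss rates below are assumptions.

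**Reproducing the plan.** After k events in n patients the safety posterior is Beta(0.05 + k, 0.95 + n − k). The smallest k that meets 70% is 2 at n = 3–4, 3 at 5–7, 4 at 8–11, 5 at 12–14 and 6 at 15–16. This matches every printed cell of Table 10.1, which prints nothing for n = 12–15. Exact recursion over these looks, against Table 10.2:

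| True rate | Calculated stop | Table 10.2 |
|---|---|---|
| 0.15 | 16.3% | 15.8% |
| 0.20 | 29.3% | 29.3% |
| 0.25 | 44.3% | 43.1% |
| 0.30 | 59.4% | 60% |
| 0.35 | 72.8% | 72.8% |

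The plan's figures are sound. The question is who enters them.

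**One patient.** Suppose 16 are treated and 6 have a DLT, one of whom leaves before the boundary is reached.
- DLT kept: 6/16, posterior 0.818, suspend.
- Patient dropped: 5/15, posterior 0.696, continue.
- Patient dropped and replaced by one without a DLT: 5/16, posterior 0.641, continue.

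**Across looks.** Take a count exactly on the boundary and remove one DLT patient, giving (k − 1)/(n − 1). The decision changes at 10 of the 14 looks: n = 4, 6, 7, 9, 10, 11, 13, 14 and 16, plus n = 3, where only two patients remain and the rule is not yet active. The results at n = 13 and 14 use derived cells that Table 10.1 does not print.

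**Stopping probability.** Let a share s of DLT patients and a share l of the others leave, be dropped and be replaced. The apparent rate is p(1 − s) / [p(1 − s) + (1 − p)(1 − l)]. With p = 0.35:

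| s | l | Apparent rate | Stop |
|---|---|---|---|
| 0 | 0 | 0.350 | 72.8% |
| 10% | 0 | 0.326 | 66.8% |
| 20% | 0 | 0.301 | 59.7% |
| 20% | 10% | 0.324 | 66.1% |
| 10% | 10% | 0.350 | 72.8% |

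The 10% and 20% echo the plan's overall drop-out rate and its 4-in-20 allowance; neither is specific to DLT patients. The formula removes each lost DLT from every look, so for a given s and l the fall shown is the largest possible.

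**Feasibility event.** Suppose that of 16 patients 5 have delayed surgery, and one more does not complete preoperative treatment but has surgery on time. The Table 10.5 label gives 5/16, posterior 0.651 (continue). The 12.2.1 event gives 6/16, posterior 0.825 (pause).

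**Table 10.5 against its own rule.** 3/8 gives 0.705, 4/11 gives 0.735 and 5/15 gives 0.706. All three exceed 70%, but the table requires 4, 5 and 6 at those sample sizes.

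**The case against.** A reader might infer that the plan deletes DLTs from its co-primary safety endpoint and so biases the result toward safe. The documents do not support that. The synopsis and the Table 10.1 label point to treated patients, adverse events are monitored continuously in everyone, and 6.3 does not replace a patient who leaves because of a DLT. Section 12.2.1 uses the word evaluable only for feasibility; the link from 12.1 to the reported safety rate is only its remark about patients being available for analysis. Bias would also require patients with a DLT to leave more often than others, which no section suggests.

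The timing point also stands. Accrual is suspended when the criterion is met, and nothing provides for reversing a crossing, so a DLT patient who leaves afterwards does no harm to the stopping decision. Other provisions limit the loss of information: 3.1.6.2 seeks peri-operative information from outside physicians, 4.5 has the investigator follow up adverse events after withdrawal of consent, and 9.3.1 asks for every effort to resolve events. Complete toxicity follow-up is itself undefined and need not mean attending every visit.

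What the objection does not remove is the contradiction. Two denominators are in force for one rule, and the one in the governing definition has no clause that keeps an observed event. The conflict between 4.2 item 27 and 4.6 is plain on the page.

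**Conclusion.** The concern holds as an inconsistency in who is counted, with one reading that lets an observed DLT leave the stopping count and possibly the reported rate. One such patient can turn a suspension into continuation, but only if they leave before the boundary is crossed.

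The effect on stopping probability rests on assumed loss rates. At a true 35%, if 10% or 20% of DLT patients and nobody else were lost from every look, stopping would fall from 72.8% to no lower than about 67% or 60%. Equal loss in both groups would not change it. These figures show sensitivity; they do not predict what will happen. Crossing a boundary leads to suspension and review, not automatic termination.

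The conflicts among the replacement rules hold on the text alone. The two feasibility points are separate: the mismatch between the Table 10.5 label and 12.2.1 may be shorthand but should be settled, and the departures at n = 8, 11 and 15 are arithmetic.

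**What to change.** 1. In 12.1, and by reference in 3.1.2 and 6.3, state that any treated patient with a DLT or treatment-related grade 5 adverse event is evaluable and counts as an event, whether or not later follow-up is complete.
2. State one safety denominator and use it in the synopsis, 12.2.2, 12.3.1 and Table 10.1. The follow-up condition may stay for patients without a DLT, with the all-treated rate as a sensitivity analysis.
3. State that replacement adds a patient and does not remove the replaced patient's observed data from the safety or feasibility counts. Base the boundaries on the first 16 evaluable patients, or extend the rows. By the stated rule, safety would need 6 of 17–18 and 7 of 19–20.
4. Reconcile 4.2 item 27 with 4.6, and 3.1.2 and 6.2.3.3 with 6.3.
5. Align the Table 10.5 event with 12.2.1 and recompute the table from the stated 70% rule.

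**Cost.** Wording and minor recalculation; reported rates may be slightly less favourable. The denominator in item 2 is a genuine trade-off. Dropping early leavers without a DLT while keeping all DLTs errs toward suspension. The apparent rate becomes p / [p + (1 − p)(1 − l)], so with l = 10% or 20% stopping rises from 44.3% to 50.5% or 57.7% at a true 25%, and from 16.3% to 19.6% or 23.9% at a true 15%. Keeping every dosed patient errs the other way: if 10% or 20% leave before a DLT is seen, the apparent rate is p(1 − l), and stopping at a true 35% falls from 72.8% to 63.7% or 53.5%.

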12.2. Study Endpoints Definition

12.2.1. Primary Endpoints

Safety of durvalumab monothererapy (cohort 1) +/- durvalumab+tremelimumab (cohort 2) administered preoperatively together with thoracic radiation in stage III NSCLC.

Safety will be measured by the frequency of any of the following events:

• Drug-related adverse events occurring up to 100 days after the last dose of immunotherapy or 30 days after surgery (whichever is longer).

18-Nov-2020 Page **114** of **164**

- Serious adverse events occurring up to 100 days after the last dose of immunotherapy or 30 days after surgery (whichever is longer).
- Clinical laboratory test by worst toxicity grade (as assessed at the time intervals outlined in the Schedule of Assessments, Figure 1.)

Feasibility of preoperative administration of durvalumab monothererapy (cohort 1) +/- durvalumab+tremelimumab (cohort 2) concurrently with thoracic radiation in stage III NSCLC

Feasibility will be evaluated through the proportion of evaluable patients who successfully complete preoperative treatment and proceed to surgery without any extended treatment-related delays defined as >8 weeks from the last day of thoracic radiation.

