Patients with a history of prior thoracic radiation or interstitial lung disease/pneumonitis will be excluded. Patients who would require a pneumonectomy will be excluded. This study aims to determine if immunoradiation will be safe, tolerable and feasible to administer prior to surgical resection for patients with stage III NSCLC. Safety will be determined by the number of dose-limiting toxicities that delay the time to surgery by >8 weeks from the date of completion of thoracic RT, and pre-defined grade 3+ pulmonary toxicities that occur during the DLT observation period in comparison to historic norms of pulmonary toxicities seen with chemoradiation prior to surgery . Feasibility will be defined as the number of patients who undergo surgery within the planned surgical window: 6-8 weeks after completion of thoracic RT. The DLT observation window will start from the day of commencement of immunotherapy, until 30 days after thoracic surgery or 100 days after the last dose of immunotherapy, whichever is longer.

From a translational perspective, this study will allow investigators to collect pre- and post-treatment tumor and lymph node tissue and serial blood and related biospecimens, aimed at examining potential mediators of response and resistance to immunoradiation. Other endpoints of clinical interest will include: pathologic response, radiologic response, recurrence-free survival (RFS), overall survival (OS) and surgical morbidity and mortality. Patients will undergo routine screening investigations including CBC, CMP, Hepatitis B/C/HIV assessment, urine, pregnancy test, and standard radiologic body imaging and brain imaging at least 28 days prior to enrollment. Patients will be monitored with a clinical visit with a study doctor, AE assessment and routine laboratory tests (CBC, CMP, endocrine labs) at each week of thoracic RT and dose of immunotherapy and at a pre-surgical and post-surgical visits. After completion of study therapy, patients will be followed every 12 weeks (+/-7 days) for 12 months with standard radiologic imaging, laboratory tests and an AE assessment, and then every 12 weeks (+/-7 days) for years 2 and 3 to assess survival status.

of Patients (planned):

Cohort 1: Identify 20 eligible and evaluable subjects, enroll 16 subjects. Cohort 2: Identify 20 eligible and evaluable subjects, enroll 16 subjects.

Inclusion Criteria:

- Written informed consent and any locally-required authorization obtained.

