Formal verification of eligibility criteria	х								
Clinical Procedures/Assessments									
Demographics including alcohol and tobacco use	Х								
Medical and Surgical History	Х							Х	Х

Trial Period:	Screening Phase	(Treat	nent Phas ment Cycl		End of Trea	atment Pha	ise		
		Thoracic Radiation Week 1-5±2							
Treatment Cycle/Title:	Study Screening (Visit 1)	1	2	3	Pre- Surgery 1	Pre- Surgery 2	Time of Surgery	Safety Follow-up	
Day	-1 to -28	1	30	60					
Scheduling Window (Days):	-28 to -1	± 3	± 3	± 3	Within 7 days of planned surgery	Within 72 hours of planned surgery		30 days post- Surgery** (± 3)	100 days post- Surgery** (± 7)
Week	-4 to -1	1	4	8	11-15	11-15		4 weeks post Surgery	3 months post surgery
Prior and Concomitant Medication Review	х	Х	х	Х	Х	Х		Х	Х
Review Adverse Events	Х	Х	Х	Х	Х	Х		Х	Х
Full Physical Examination	Х	Х	X	Х	Х				
Survival Status Assessment (Telephone)									
Vital Signs (pre-, during and post- infusion vital signs assessments) ¹	х	х	х	Х	х	Х		Х	Х
Weight	Х	Х	Х	Х	Х				
ECOG Performance Status	Х	Х	Х	Х	Х				
EKG ²	Х	Х	X ²	X ²	X ²				
Durvalumab Administration		Χ	Х	Χ					

Trial Period:	Screening Phase	Treatment Phase (Treatment Cycle				End of Treatment Phase				
		Thoracic Radiation Week 1-5±2								
Treatment Cycle/Title:	Study Screening (Visit 1)	1	2		3	Pre- Surgery 1	Pre- Surgery 2	Time of Surgery	Safety Follow-up	
Day	-1 to -28	1	30		60					
Scheduling Window (Days):	-28 to -1	± 3	± 3		±3	Within 7 days of planned surgery	Within 72 hours of planned surgery		30 days post- Surgery** (± 3)	100 days post- Surgery** (± 7)
Week	-4 to -1		L	4	8	11-15	11-15		4 weeks post Surgery	3 months post surgery
Tremelimumab Administration										
(cohort 2 only) Laboratory Procedures/Assessmer	l nts³							 		
Hepatitis B, C, HIV	Х									
Pregnancy Test – Urine or Serum 2-HCG ⁴	х	х	х			х		х	Х	Х
Serum Chemistries, Thyroid Function Tests, Liver Function Tests	х	х	х		х	х	Х	х	X	Х
Coagulation parameters (PT/INR and aPTT)	Х						Х	х	X	Х
Hematology	Х	Х	Х		Х		Х	Х	Х	Х
Thyroid function tests (TSH and fT3 and fT4) ⁵	Х		х				Х	х	Х	Х

Trial Period:	Screening Phase	Treatment Phase (Treatment Cycles				End of Treatment Phase				
Thoracic Radiation Week 1-5:		tion	2							
Treatment Cycle/Title:	Study Screening (Visit 1)	1	2		3	Pre- Surgery 1	Pre- Surgery 2	Time of Surgery	Safety Follow-up	I
Day	-1 to -28	1	30		60					

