Before study entry, throughout the study, and following study drug discontinuation, various clinical and diagnostic laboratory evaluations are outlined. The purpose of obtaining these detailed measurements is to ensure adequate safety and tolerability assessments. Clinical evaluations and laboratory studies may be repeated more frequently if clinically indicated. The Schedule of Assessments during the screening and treatment period (Figure 1) is provided following the Protocol Synopsis.

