8.1.2. Treatment Phase

Procedures to be conducted during the treatment phase of the study are presented in the Schedule of Assessments. Screening procedures performed within 28 days of Cycle 1 Day 1 (C1D1) do not need to be repeated.

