8.2.5. Clinical laboratory tests

The following clinical laboratory tests will be performed at the study sites of local laboratories, as deemed appropriate by the study investigator (see the Schedule of Assessments). Laboratory values outside of reference ranges will be reported to the study investigator, and treatment may be held, deferred or discontinued if necessary.

- Coagulation parameters: Activated partial thromboplastin time and International normalized ratio to be assessed at baseline and as clinically indicated
- Pregnancy test (female subjects of childbearing potential only)
- Urine human chorionic gonadotropin
- Serum beta-human chorionic gonadotropin (at screening only)
- Thyroid Stimulating Hormone
- o free T3 and free T4 only if TSH is abnormal

18 November 2020 Page **86** of **164**

- o Serum Chemistries
- Liver function tests
- Other laboratory tests
 - Hepatitis A antibody, hepatitis B surface antigen, hepatitis C antibody
 - HIV antibody

TABLE 6. HEMATOLOGY LABORATORY TESTS

Basophils Mean corpuscular volume

Eosinophils Monocytes

Hematocrit Neutrophils

Hemoglobin Platelet count

Lymphocytes Red blood cell count

Mean corpuscular hemoglobin Total white cell count

Mean corpuscular hemoglobin concentration

TABLE 7. CLINICAL CHEMISTRY (SERUM OR PLASMA) LABORATORY TESTS

Albumin	Lipase ^b	
Alkaline phosphatase	Magnesium ^c	
ALT ^a	Potassium	
Amylase ^b	Sodium	
AST ^a	Total bilirubin ^a	
Bicarbonate ^c	Total protein	
Calcium	TSH	
Chloride ^c	T3 free ^c (reflex)	
Creatinine clearance ^c	T4 free ^c (reflex)	

18 November 2020 Page **87** of **164**

Creatinine	Urea or blood urea nitrogen, depending on local
	practice

Gamma glutamyl-transferase^c

Glucose

Lactate dehydrogenase

- Tests for ALT, AST, alkaline phosphatase, and total bilirubin must be conducted and assessed concurrently. If total bilirubin is $\ge 2 \times$ upper limit of normal (and no evidence of Gilbert's syndrome) then fractionate into direct and indirect bilirubin.
- It is preferable that both amylase and lipase parameters are assessed. For sites where only 1 of these parameters is routinely measured then either lipase or amylase is acceptable.
- Bicarbonate (where available), chloride, creatinine clearance, gamma glutamyltransferase, and magnesium testing are to be performed at screening, on Day 0 (unless screening laboratory assessments are performed within 3 days prior to Day 0), and if clinically indicated.

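### The synopsis requires weekly visits and laboratory tests during radiation, but Figure 1, which Section 12.2.1 cites, schedules no draw between Day 1 and Day 30, and no text says which governs

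*Combined protocol and SAP*

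**What the plan says.** **Synopsis, Methodology.** Patients have a clinic visit with a study doctor, an adverse event assessment and "routine laboratory tests (CBC, CMP, endocrine labs) at each week of thoracic RT and dose of immunotherapy".

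**Figure 1 (Schedule of Assessments).** The treatment-phase columns are cycles 1, 2 and 3, on Days 1, 30 and 60, each ±3 days. The row "Serum Chemistries, Thyroid Function Tests, Liver Function Tests" and the hematology row are marked at those visits. Radiation appears only as a header over the cycle columns and is not divided into weeks. Footnote 3 waives the Day 1 repeat when screening bloods are recent and requires results to be reviewed before each infusion. No footnote adds weekly tests.

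**Sections that point to Figure 1.** Section 8.1.2: "Procedures to be conducted during the treatment phase of the study are presented in the Schedule of Assessments". Section 8.2.5 has the tests done "as deemed appropriate by the study investigator (see the Schedule of Assessments"). Section 12.2.1 defines the third safety component as "Clinical laboratory test by worst toxicity grade (as assessed at the time intervals outlined in the Schedule of Assessments, Figure 1").

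**Section 6.3.** Among the DLTs is "Liver transaminase elevation > 8 × ULN or total bilirubin > 5 × ULN". The consequence is stated: "A patient who experiences a DLT will be permanently discontinued from treatment".

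**The concern.** Two parts of one protocol give different laboratory schedules for the same weeks, and the sections on conduct and on the endpoint cite the sparser one. A worst-grade summary depends on how often blood is drawn, so the choice of schedule affects what the endpoint can record.

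The weeks in question follow the first dose, when immunotherapy and radiation run together. Section 1.13.1 lists raised transaminases as an identified durvalumab risk. Section 1.13.3 lists raised ALT, amylase and lipase among events seen in at least 10% of patients on the combination. Such changes can occur without symptoms. If a transaminase or bilirubin peak that meets Section 6.3 is never measured, a patient who should stop treatment can receive dose 2. The event is also missing from the DLT count, for which Section 12.2.2 names liver toxicity as a concern.

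**Working it through.** The plan states no figure on this point to reproduce. The check compares the schedules and counts draws.

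**1. Length of the gap in Figure 1.** Dose 1 is on Day 1 and the next scheduled draw is on Day 30 ±3, that is Days 27 to 33.
- Shortest: 27 − 1 = 26 days.
- Longest: 33 − 1 = 32 days.

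**2. Position relative to radiation.** Section 6.2.2.3 gives 25 fractions at 5 per week: 25 / 5 = 5 weeks. Figure 1 also shows weeks 1–5 (±2). On that dating Day 30 falls in week 5. Section 6.2.1 instead ends radiation on Days 25–28, so the nominal Day 30 draw comes 30 − 28 = 2 to 30 − 25 = 5 days after radiation. On either dating, weeks 2 to 4 have no scheduled draw.

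**3. Draws between Day 1 and Day 30, undelayed course.**

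| Source | Scheduled draws |
|---|---|
| Synopsis | about 3 (weeks 2, 3 and 4) |
| Figure 1 | 0 |

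**4. Whether other text fills the gap.**
- Section 8, opening: "Clinical evaluations and laboratory studies may be repeated more frequently if clinically indicated". This is discretionary and does not reach a patient without symptoms.
- Section 3.1.6.2 (weekly record review) and Section 9.1.4 (weekly grading of radiation events) call for no blood draw.
- Footnote 3 of Figure 1 (review before infusion) catches an abnormality that persists to dose 2, but not one that has recovered.
- Section 9.3.12.2 (Hy's Law) applies at any time on study medication, but needs a test to be triggered.
- Section 9.3.5 reports deterioration in a mandated laboratory value as an adverse event only if it is serious or leads to discontinuation, or through associated signs and symptoms. Asymptomatic changes therefore depend largely on the laboratory component.

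**5. Blood volume.** Table 9 allows 5 mL for chemistry and 5 mL for hematology per sample. Three extra sets: 3 × (5 + 5) = 30 mL, and 30 / 670 = 4.5% of the Table 9 total.

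**6. State of Table 9.** It plans 7 chemistry and 7 hematology samples. Figure 1, in the text available, carries 9 and 8 marks, or 8 and 7 if footnote 3 lets screening bloods stand for Day 1. The long-term follow-up table marks serum chemistry at months 6, 9 and 12 as well. Table 9 counts three 120 mL biomarker draws. Section 8.5.1 lists four (Day 1; 30 days and 100 days after surgery; 12 months), so the biomarker volume is 4 × 120 + 3 × 80 = 720 mL, against 3 × 120 + 3 × 80 = 600 mL in Table 9.

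**The case against.** The strongest reply is that nothing in Figure 1 forbids weekly tests. The synopsis is part of the protocol, so a site following the whole document draws them and Figure 1 is merely incomplete. This stands in part: the harm arises only where a site works from Figure 1. But Section 8.1.2 sends sites there for treatment-phase procedures.

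Figure 1 was also read from broken table text. The tremelimumab row, for example, carries no marks although dosing in cohort 2 is certain. Exact mark counts therefore deserve caution. The absence of a weekly column is more secure, because Sections 3.1.4 and 6.2.1 repeat the Day 1, 30 and 60 dosing structure and no footnote adds tests.

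The chain of harm is narrow. The abnormality must arise after dose 1, cause no symptoms, prompt no test, and recover untreated before the dose 2 review. Section 6.3 also asks for repeat testing before a laboratory finding without a clinically significant abnormality is called a DLT. Appendix 1 manages elevations of this size with intravenous steroids tapered over at least 28 days, which does not suggest that rapid untreated recovery is usual. All of this stands and limits the weight of the point.

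A reader might infer more than the documents support:
- *That patients go unmonitored during radiation.* The synopsis requires weekly monitoring.
- *That the safety result is biased by a calculable amount.* A detection probability needs event durations and frequencies, and the documents give none.
- *That the stopping rules or primary analysis are wrong.* The boundaries in Section 12.2.2 and the analysis in Section 12.3.1 are unchanged.
- *That Section 12.2.1 excludes off-schedule results.* Its parenthesis can equally be read as describing when tests are planned.

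**Conclusion.** The inconsistency is real and should be corrected. Figure 1 has no scheduled draw for 26 to 32 days after dose 1, against about 3 under the synopsis, and no text settles which applies. If sites follow Figure 1, a transient asymptomatic laboratory toxicity can be missed, including a DLT that should end treatment. Dose 2 could then be given and the event not counted.

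This assumes that some sites follow Figure 1, that dose 2 is given in its window, and that no clinically indicated test is done in between. How often the sequence would occur is unknown. The importance is minor to moderate: an operational gap in a study whose primary aim is safety, not a fault in its statistical design.

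**What to change.** **(a) Figure 1.** Add the synopsis's weekly study-doctor visit, adverse event assessment and blood tests (CBC, CMP, endocrine) for each week of thoracic radiation actually delivered. Fixed days would not serve, because radiation may run to weeks 1–5 ±2 and Section 3.1.5 lets dose 2 be deferred within it. Deleting the weekly tests from the synopsis would also remove the inconsistency, but would leave the gap.

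**(b) Table 9.** Recount it from the corrected Figure 1, the long-term follow-up table and Section 8.5.1. Do not simply add 30 mL to the present total, since the biomarker rows also disagree with Section 8.5.1.

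**(c) Section 12.2.1.** Define the laboratory component as *the worst CTCAE grade over all laboratory results, scheduled or unscheduled, from first dose to the end of the Section 6.3 DLT window*. Add a supplementary table restricted to scheduled results.

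**Cost.** About 3 extra draws and 30 mL per patient before Day 30 in an undelayed course, already promised in the synopsis, from patients attending five days a week for radiation. The rest is wording and one table. Reported worst grades may be somewhat higher and will depend partly on how often a patient is tested; the scheduled-only table lets a reader judge that.
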